### 8.2.3 Data and Safety Monitoring Plan

*Cross-reference: UNC IRBIS Application A.7.2, C.1.1.*

The study team has developed and finalized a DSMP. This plan will adhere to the PCORI guidelines on DSMPs.

## 8.3 Adverse Event/Serious Adverse Event monitoring and reporting procedures

An AE is any untoward or unfavorable medical occurrence in a human subject, including any abnormal sign (for example, abnormal physical exam or laboratory finding), symptom, or disease temporally associated with the subject's participation in the research, whether or not considered related to the

subject's participation in the research (modified from the definition of AEs in the 1996 International Conference on Harmonization E-6 Guidelines for Good Clinical Practice).

An SAE is an AE that meets any one of the following criteria: results in death, is life threatening, or requires inpatient hospitalization or causes prolongation of existing hospitalization, results in persistent or significant disability/incapacity, birth defects or based on medical judgement may jeopardize the participants health or may require medical or surgical intervention. This study does not involve an investigational product, device intervention, or highly invasive data collection procedure. However, recognizing that unanticipated events (see below) can occur during any study, the following reporting protocols will apply.

Study participation and exposure to the interventions are expected to have a moderately low risk of AEs for participants, in the form of adverse effects associated with reduction of opioid dosage. At the same time, the underlying chronic conditions of the participants may naturally lead to deleterious health outcomes. To efficiently collect safety information that is relevant to study participation and the interventions, detailed information concerning a prespecified set of AEs and SAEs will be collected and evaluated throughout the conduct of the trial.

### 8.3.1 Reportable Adverse Events and Serious Adverse Events

For the purposes of this study, an event will be considered *reportable (collected for data entry)* if it meets at least one of the criteria below. The AEs and SAEs shown in **Table 11** will be recorded and reported. SAEs not on this list will not be recorded or reported.

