#### 8.1.5 Potential Physical Risks

*Cross-reference: UNC IRBIS Application section A.6.9, A.6.10.*

There is some potential risk that participants may experience increased pain if they reduce or discontinue their opioid medication.

We expect any side effects to be rare or infrequent and mild-to-moderate.

This study is comparing two different behavioral interventions for patients with chronic pain who are already on chronic opioid therapy. Some of the intervention content is about tapering or discontinuing opioids. The participant may choose to request to taper or discontinue opioids. Lowering the dose of opioids has the potential for side effects from withdrawal. But, there are no extra risks from this study compared to discontinuation as part of usual care.

The approach of this trial is to promote a controlled opioid reduction, which in some cases might lead to complete discontinuation, with a patient's consent. The protocol does not specify or foresee abrupt tapering.

If patients do choose to taper, the physicians will be doing a very gradual taper of their opioids (as per CDC guidelines, 10% per week), which has rare to infrequent risk of withdrawal. If withdrawal is experienced, mild to moderate symptoms are expected. These symptoms may include low energy; irritability; anxiety; agitation; insomnia; sweats; muscle aches and pain; as well as abdominal cramping, nausea, and vomiting. Patients will be advised to call their provider if they experience symptoms of withdrawal.

To reduce physiological risk, certain safeguards will be implemented at RTI and at all clinical institutions. Procedures to reduce clinical risk include intensive medical monitoring of AEs and medical management common for this study population.

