**Table 11. Reportable Events and Assessment Methods**

Reportable Event	Assessment Method
Suicide risk (active suicidal ideation or attempted suicide) (see section 8.3.5 below)	Adverse Event Case Report Form
All Deaths (including opioid-related, suicide, and all other deaths)	Adverse Event Case Report Form, PCORnet EHR-based data, National Death Index (available after study completion), publicly available data
Hospitalizations or Emergency Department (ED) visits related to opioid use (overdose or withdrawal) or related to suicide attempt	Adverse Event Case Report Form, PCORnet EHR-based data, patient self-report via 6- and 12-month follow-up surveys

When one of these AEs is identified, the institution PI or designee will assess the event to evaluate whether it is one of the following:

- Unanticipated (i.e., unexpected). These events are AEs that are new or greater than previously known, in terms of nature, severity, frequency or occurrence, as documented in the protocol, consent, or other study documents approved by the IRB (OHRP-  
<https://www.hhs.gov/ohrp/regulations-and-policy/guidance/reviewing-unanticipated-problems/index.html>).
- Related (possibly related, probably related, or definitely related) to study participation.

Institutions will record all reportable events in REDCap in the Adverse Event Case Report Form.

Reporting will either follow an expedited or periodic timeline.

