### 8.3.2 Expedited Reporting

Expedited reporting procedures must be followed when an SAE meets both of these conditions:

- SAE is considered **unanticipated/unexpected**, AND
- at a minimum, **possibly related** to study participation.

Institutions must report expedited SAEs within 2 business days of the Institution's awareness to the single UNC IRB and to RTI. RTI must notify DSMB of the event within 24 hours. RTI must provide a summary report of the event to DSMB within 7 days.

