### 8.3.4 Unanticipated Problems

The study will collect and report unanticipated (i.e., unexpected) problems that may involve risk to the participant or study staff, but do not necessarily result in an AE (i.e., harm). An example of an unanticipated problem that may not result in an AE is misplacement of a participant's research record containing PII such that the risk of loss of confidentiality is introduced. This event is reportable regardless of whether the confidentiality is breached or not breached.

Institutions must report other unanticipated problems that are not SAEs but involve substantial harm (or genuine risk of substantive harm) to the safety, rights, or welfare of the institution's research participants, research staff, or others to the single UNC IRB and RTI within 5 business days.

Otherwise, the institution will report unanticipated problems to the single IRB and RTI on an annual basis at the time of continuing review.

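### The closed list of reportable events in Protocol 8.3.1 has no exception for a non-fatal, off-list SAE that is unanticipated and possibly related, so such an event has no explicit route to expedited reporting

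*Protocol*

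**What the plan says.** Protocol 8.3 defines an SAE in general terms: an adverse event that "results in death, is life threatening, or requires inpatient hospitalization or causes prolongation of existing hospitalization", with disability, birth defects and medical judgement as further grounds. It explains why reporting rules are needed even without an investigational product: "recognizing that unanticipated events (see below) can occur during any study, the following reporting protocols will apply". It then narrows collection, so that "detailed information concerning a prespecified set of AEs and SAEs will be collected and evaluated throughout the conduct of the trial".

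Protocol 8.3.1 makes that narrowing absolute: "SAEs not on this list will not be recorded or reported". Table 11 has three rows: suicide risk; all deaths; and hospitalizations or ED visits related to overdose, withdrawal or a suicide attempt. The text under the table asks the institution PI or designee to judge unexpectedness and relatedness when one of these listed events is identified.

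Protocol 8.3.2 says "Expedited reporting procedures must be followed when an SAE meets both of these conditions": the event is unexpected, and at least possibly related to participation. The deadlines are two business days to the single IRB and the coordinating centre, a further 24 hours to the DSMB, and seven days for a summary report.

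Protocol 8.3.4 provides a five-business-day route: "Institutions must report other unanticipated problems that are not SAEs but involve substantial harm". Remaining unanticipated problems are reported once a year.

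SAP 9.2 repeats the restriction to three adverse event types. SAP 9.7 summarises those types and also plans a count of participants with any SAE.

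**The concern.** The protocol describes unanticipated events as new, or greater than previously known in nature, severity or frequency. A list fixed in advance is poorly suited to the first kind. The expedited route is meant to bring such events quickly to the IRB and DSMB, but entry to it depends on recording and assessment steps that the closed list withholds from anything not foreseen.

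Participant protection is at stake first. If either intervention caused a serious non-fatal harm that nobody had listed, a site following 8.3.1 literally would not enter it on a form, would not be asked whether it was related, and would not send it on promptly. The final report is affected second: a line headed any SAE in SAP 9.7 could be read as total SAEs when only the listed kinds were collected.

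**Working it through.** No sample size, power or rate enters this point, so there is nothing to recompute. The check follows one test event through the text: a non-fatal inpatient admission that is not due to overdose, withdrawal or a suicide attempt, involves no active suicidal ideation, and would be judged unexpected and possibly related if anyone were asked.

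1. **Is it an SAE?** Yes. Inpatient hospitalization is enough under Protocol 8.3.
2. **Is it in Table 11?** No. It is not suicide risk and not a death, and the hospitalization row is limited to causes that do not apply.
3. **Is it recorded?** No. Protocol 8.3.1 excludes it from both recording and reporting.
4. **Is it assessed for unexpectedness and relatedness?** Not by any stated step. That assessment starts only from a listed event.
5. **Does 8.3.2 catch it?** This depends on what an SAE means there. If it means any SAE, 8.3.2 calls for a report that 8.3.1 rules out. If it means a reportable SAE, the sections agree and the event falls outside both. Neither reading gives a site an explicit instruction to record it and send it on.
6. **Does 8.3.3 catch it?** No. Periodic reporting there requires that the SAE is not related.
7. **Does 8.3.4 catch it?** Not within five business days, because that rule is for problems that are not SAEs. The residual annual clause could be read to include it, and it names the IRB and the coordinating centre but not the DSMB. An event just after one continuing review could wait about 12 months, against two business days under 8.3.2.
8. **Does it reach the DSMB otherwise?** Protocol 8.2.2 builds the DSMB report from adverse event data reported in REDCap. An event kept off the form does not enter that report.
9. **Is there any other trace?** Possibly. Protocol 3.12 records reasons for withdrawal, and Protocol 4.1.4 extracts health care visits. Neither starts an SAE review. Protocol 3.7 asks for any SAE, but only among people who consent and are not randomized.
10. **Does the SAP add a catch-all?** No. SAP 9.2 and 9.7 keep the three types.

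As a control, take a death from any cause or an overdose admission. It is listed, so it is recorded and assessed, and it goes to 8.3.2 if unexpected and at least possibly related. The route works for listed events. The gap is confined to non-fatal, off-list SAEs.

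**The case against.** The strongest reply is that targeted collection is deliberate and reasoned. Protocol 8.3 points to the lack of an investigational product, to underlying chronic conditions that produce serious events of their own, and to efficient collection of relevant safety data. The SAP follows the same scope. That stands: nothing here argues for collecting every SAE.

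Several stronger readings are tempting, and the documents do not support them.

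- A reader might infer that 8.3.1 and 8.3.2 cannot both be obeyed. Read in order, 8.3.1 defines what is reportable and the next two sections sort those events by timeline, so an SAE in 8.3.2 can mean a reportable one. The contradiction is possible but not forced.
- A reader might infer that no unforeseen event can be expedited. All deaths are listed, and a listed event can itself be unanticipated through its severity or frequency.
- A reader might infer that the IRB never learns of an off-list event. The annual clause may still bring it there, late.
- A reader might take an admission for pain after a dose reduction as the obvious example, since Protocol 8.1.5 says "There is some potential risk that participants may experience increased pain if they reduce or discontinue their opioid medication". But Protocol 6.2.1 gives a temporary rise in pain as an example of a withdrawal symptom, and 8.1.5 includes muscle aches and pain among such symptoms, so the withdrawal row of Table 11 may cover it.
- A reader might want a count of missed events. Neither document gives a rate for off-list related SAEs, so any count would rest on an unsupported assumption.

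The Safety Protocol, the Data and Safety Monitoring Plan and the DSMB Charter are not part of the text reviewed and may contain a catch-all. If they do, the explicit exclusion in 8.3.1 still conflicts with it and needs correcting.

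**Conclusion.** The point holds in limited form. For a non-fatal SAE outside Table 11 that is unanticipated and at least possibly related, the protocol provides no explicit recording step, no assessment step and no prompt reporting route; at best the event appears in an annual report. This follows from the wording of 8.3.1, the text under Table 11, and 8.3.4, and it holds on either reading of 8.3.2. Its size is a class of event rather than a number: every SAE of this class is outside routine capture by rule, and its frequency cannot be estimated from the documents. The primary and secondary effectiveness analyses are untouched. The matter is worth correcting because it concerns participant protection and the exception costs little.

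**What to change.** Keep the targeted list and reconcile Protocol 8.3.1 to 8.3.4 so that they state one rule. Replace the blanket exclusion with text to this effect: *SAEs outside this list are not collected routinely. Any other SAE that the institution PI or designee learns of and judges both unanticipated and at least possibly related to study participation is entered on the Adverse Event CRF and reported under 8.3.2.* State that the assessment under Table 11 applies to such events too, and add a matching row to Table 11.

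In the SAP, add the same category to the 9.7 summary and to the 9.2 definition, and label the any-SAE line as limited to the collected categories. The label is useful even if no events are added.

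The cost is a short IRB amendment, one table row and a few more event forms. There is a limit of timing. SAP 4.6 expects the last intervention visits by March 2023, and SAP 6 already reports final enrolment and a June 2023 DSMB report. For completed follow-up, the change can bring in only events that sites already know of, and the report should say so.

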**Table 11. Reportable Events and Assessment Methods**

Reportable Event	Assessment Method
Suicide risk (active suicidal ideation or attempted suicide) (see section 8.3.5 below)	Adverse Event Case Report Form
All Deaths (including opioid-related, suicide, and all other deaths)	Adverse Event Case Report Form, PCORnet EHR-based data, National Death Index (available after study completion), publicly available data
Hospitalizations or Emergency Department (ED) visits related to opioid use (overdose or withdrawal) or related to suicide attempt	Adverse Event Case Report Form, PCORnet EHR-based data, patient self-report via 6- and 12-month follow-up surveys

When one of these AEs is identified, the institution PI or designee will assess the event to evaluate whether it is one of the following:

- Unanticipated (i.e., unexpected). These events are AEs that are new or greater than previously known, in terms of nature, severity, frequency or occurrence, as documented in the protocol, consent, or other study documents approved by the IRB (OHRP-  
<https://www.hhs.gov/ohrp/regulations-and-policy/guidance/reviewing-unanticipated-problems/index.html>).
- Related (possibly related, probably related, or definitely related) to study participation.

Institutions will record all reportable events in REDCap in the Adverse Event Case Report Form.

Reporting will either follow an expedited or periodic timeline.

### 8.3.2 Expedited Reporting

Expedited reporting procedures must be followed when an SAE meets both of these conditions:

- SAE is considered **unanticipated/unexpected**, AND
- at a minimum, **possibly related** to study participation.

Institutions must report expedited SAEs within 2 business days of the Institution's awareness to the single UNC IRB and to RTI. RTI must notify DSMB of the event within 24 hours. RTI must provide a summary report of the event to DSMB within 7 days.

### 8.3.3 Periodic (Non-Expedited) Reporting

Periodic (Non-Expedited) reporting procedures must be followed when the SAE meets both of these conditions:

- SAE is considered unanticipated/unexpected OR expected AND
- SAE is NOT related to study participation.

RTI must provide a summary report of the event to DSMB at the next DSMB meeting as part of the regular DSMB meeting report.

### 8.3.4 Unanticipated Problems

The study will collect and report unanticipated (i.e., unexpected) problems that may involve risk to the participant or study staff, but do not necessarily result in an AE (i.e., harm). An example of an unanticipated problem that may not result in an AE is misplacement of a participant's research record containing PII such that the risk of loss of confidentiality is introduced. This event is reportable regardless of whether the confidentiality is breached or not breached.

Institutions must report other unanticipated problems that are not SAEs but involve substantial harm (or genuine risk of substantive harm) to the safety, rights, or welfare of the institution's research participants, research staff, or others to the single UNC IRB and RTI within 5 business days.

Otherwise, the institution will report unanticipated problems to the single IRB and RTI on an annual basis at the time of continuing review.

### 8.3.5 Suicidality

We will capture suicide risk (active suicidal ideation or attempted suicide) during the intervention period during clinical encounters. As this is a pragmatic unmasked behavioral intervention trial, suicide risk will only be captured if the participant indicates intent to self-harm during the clinical intervention visit; the provider will not conduct a study-specific suicide risk assessment. If the clinic becomes aware of suicide ideation, the provider will follow the institution's or clinic's protocols, as described in our **Safety Protocol** (see Appendix). Similarly, if active suicide ideation is self-reported to the research coordinator during the screening visit review of exclusion criteria, the provider will be notified and will follow the institution's or clinic's protocols.

The therapists delivering the MI +CBT-CP intervention will all be masters- or PhD-level mental health providers with training and experience handling suicidal patients. If a participant does express suicidal ideation, the therapist will handle it in the manner that they would in their clinical practice. Similarly, if a participant being seen in the SDM intervention (Arm 1) expresses suicidal ideation, the clinic will handle it in the manner that they would in their clinical practice.

The provider will report the event to the institution's Research Coordinator, and the Research Coordinator will complete an Adverse Event Case Report Form.

We will capture whether the participant has been to the ED or had an inpatient hospitalization because of self-harm via self-report and PCORNet CDM data extraction. We will capture information on when and where this occurred.

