The participant and provider will meet as often as needed for pain management. If the patient and physician decide that an opioid dose change is warranted, the patient may have more frequent visits with the SDM provider. A change in the frequency of visits due to medication changes is part of standard practice for opioid management and will be covered by health insurance. The patient may have a total of 4 to 12 visits over an approximately 12-month period. (We expect about one or more visits every 3 months to assess benefits and harms of opioid therapy. This would be for a patient on a stable dose of opioid medication who will not be adjusting the opioid dose during study follow-up. Patients who undergo opioid tapering may have more frequent follow-up visits to reinforce the provider-patient partnership, discuss potential withdrawal symptoms, such as temporary increase in pain, and assess pain and opioid management based on clinical judgement.)

If participants are assigned to Arm 1 and their provider is trained in SDM, the participant will continue seeing this provider for the 12-month intervention period. If the provider is not trained in SDM, participants will be asked to switch providers for opioid management care, and an SDM-trained provider will be assigned to the participant based on availability. In the study's consent form, participants are told about the potential need to change providers in order to receive opioid treatment from a trained provider. Participants will continue with their current PCP or another provider not trained in SDM for their non-opioid care—such as for acute or chronic conditions—with an understanding that only a provider trained in SDM can manage participants' opioid care.

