## 6.3 MI+CBT-CP Intervention

Participants in Arm 2 will receive guideline-concordant pharmacotherapy, plus an empirically-based behavioral pain management behavioral therapy intervention, including MI to enhance motivation for active participation in CBT-CP and for opioid dose reduction or cessation, and CBT-CP for pain-coping skills enhancement. The MI+CBT-CP intervention is an empirically based behavioral pain management therapy intervention. MI and CBT-CP have both been used effectively with chronic pain.

### 6.3.1 Enrollment Procedures for Arm 2

For Arm 2 participants, the GCC portion of the intervention will be delivered by the participant's primary care provider or pain specialist who is participating in the study and has been trained. The participant will continue to see the same provider for opioid management regardless of whether their provider is trained in SDM or not. Because Arm 2 participants will not receive SDM decision aids, the providers will be trained not to use SDM with these patients (even if they have been trained in SDM).

Licensed clinicians, including masters- or PhD-level psychologists, licensed clinical social workers, or licensed professional counselors, will deliver the MI+CBT-CP intervention. To verify the training of MI+CBT-CP providers, RTI will request proof/documentation of fulfilling the study's MI+CBT-CP training from each MI+CBT-CP provider. However, the MI/CBT-CP providers are clinical staff at their respective institutions and have experience with MI and CBT-CP. Thus, training will focus on the study MI/CBT-CP protocol, and not MI or CBT per se.

The intervention will include 1 individual MI session as soon as this session can be scheduled after enrollment and up to 8 CBT-CP group therapy sessions. We anticipate the MI+CBT-CP component of the intervention may occur within 3 months of enrollment but could extend longer. The process for scheduling the participant may vary slightly based on the institution or clinic. Study or clinic staff will continue to follow up with the participant until the individual MI visit and the group CBT sessions are scheduled. The goal will be to arrange for CBT to begin as soon as possible after the baseline interview.

The participant will be asked to attend one individual MI session that will last about 30 to 60 minutes, either in-person or via the clinic's telehealth platform.

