9.7 Safety and Adverse Events Analysis

AEs will be listed and summarized overall and by event term (hospitalization or emergency department visit due to opioid withdraw/overdose, suicidality, and death). The number and proportion of individuals experiencing an adverse event, any SAE, and AE by relationship to intervention will also be summarized.

Contingency table methods will be used to generate point and interval estimates of the risk of each AE type by intervention arm. Treatment groups will be compared using an unadjusted chi-squared test. Event rates are too small to stratify by clinical site. For events with expected cell counts < 5, groups will be compared with a Fisher's exact test, where specified, Binomial 95% CIs for proportions are based on the exact Clopper-Pearson method (ref Clopper, Pearson).

In SAS, using PROC FREQ:

The chi-square test and corresponding risk difference 95% CI are obtained by:

```
table Intervention *AEvar /riskdiff(method=wald equal var=null) chisq ;
```

For small expected cell counts, the exact test and risk difference 95% CI are obtained by:

```
table Intervention*AEvar / fisher; exact riskdiff (method=score);
```

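### Visit-disclosed suicide risk is ascertained through contacts that differ by arm, so the SAP's unadjusted comparison of suicidality mixes detection with harm

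*Protocol*

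**What the plan says.** Protocol 8.3.5 opens by saying that suicide risk, defined as active ideation or an attempt, is captured "during the intervention period during clinical encounters". Its next sentence is narrower: "suicide risk will only be captured if the participant indicates intent to self-harm during the clinical intervention visit", and "the provider will not conduct a study-specific suicide risk assessment". Table 11 lists suicide risk as a reportable event in its own right, with the adverse event case report form as its sole assessment method.

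A second route exists. The last paragraph of 8.3.5 captures ED attendance or admission "because of self-harm via self-report and PCORNet CDM data extraction". Table 11 lists acute care for a suicide attempt as a separate event with three sources (adverse event form, PCORnet EHR data, 6- and 12-month surveys). It lists deaths separately again, with several sources.

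The arm-specific contacts differ. For Arm 1, Protocol 6.2.1 says "The patient may have a total of 4 to 12 visits over an approximately 12-month period", conducted by the provider who manages the opioids. For Arm 2, Protocol 6.3.1 plans one individual MI session and up to eight group CBT-CP sessions: "We anticipate the MI+CBT-CP component of the intervention may occur within 3 months of enrollment but could extend longer". Under 8.3.5 the Arm 2 therapists "will all be masters- or PhD-level mental health providers with training and experience handling suicidal patients".

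SAP 9.2 makes suicidality risk one of three adverse event types. For that type SAP 9.7 says: "Contingency table methods will be used to generate point and interval estimates of the risk of each AE type by intervention arm", followed by an unadjusted chi-squared test, or Fisher's exact test when expected counts fall below 5.

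**The concern.** A count that rests on unsolicited disclosure depends on how often a participant meets someone who will record it, whether the meeting is private or in a group, and how attuned that person is to suicidality. All three differ by design between the arms. With the same true risk in both arms, the recorded counts could still differ. A real difference could also be hidden.

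In Arm 1 the contact count may also depend on the primary outcome. Protocol 6.2.1 foresees more visits when the dose is changed, so participants who taper have more opportunities to disclose.

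What is at stake is the safety statement of an opioid-reduction trial. A reported difference in suicidality, or a reassuring absence of one, could be an artefact of contact.

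**Working it through.** The documents give no rate, power or sample size for suicidality, so there is no plan figure to reproduce. The check traces the sources and then illustrates the effect under stated assumptions.

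**1. Which events depend on visits**

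| Event | Source | Depends on intervention visits? |
|---|---|---|
| Ideation; attempt without acute care | Adverse event form only (Protocol Table 11, 8.3.5) | Yes |
| ED or hospital care for self-harm or attempt | Adverse event form, EHR extraction, surveys (Protocol Table 11, 8.3.5; SAP 4.7) | Two of three sources do not |
| Death | Adverse event form, EHR, death index, public data (Protocol Table 11) | Mostly not |

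SAP 9.2 names the electronic record as a source for deaths only. SAP 4.4.1 and the SAP 4.7 flow chart foresee EHR extraction of adverse events, including acute care for a suicide attempt. If SAP 9.2 were applied literally, acute-care events would rest on the adverse event form and on surveys with about 60% completion (SAP 6).

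**2. Contacts by arm**

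- Arm 1: 4 to 12 individual visits over about 12 months (Protocol 6.2.1). SAP 5.2 expects that many participants may complete only 3.
- Arm 2: up to 1 + 8 = 9 sessions, eight of them in a group, expected within about 3 months but possibly later (Protocol 6.3.1).
- Both arms: GCC opioid-management visits for 12 months (Protocol 6). No number is given for Arm 2. Section 8.3.5 names the MI+CBT therapists and the SDM clinic, but not the separate Arm 2 opioid provider.

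**3. Effect of contact number**

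Assume each contact has the same chance *d* that an at-risk participant discloses. Detection over *k* contacts is 1 − (1 − *d*)^*k*.

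| *d* | *k* = 3 | 4 | 9 | 12 | 13 |
|---|---|---|---|---|---|
| 0.05 | 0.14 | 0.19 | 0.37 | 0.46 | 0.49 |
| 0.10 | 0.27 | 0.34 | 0.61 | 0.72 | 0.75 |
| 0.20 | 0.49 | 0.59 | 0.87 | 0.93 | 0.95 |

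At *d* = 0.10, Arm 2 with 9 sessions against Arm 1 with 3 visits gives 0.613/0.271 = 2.26 in favour of more Arm 2 events. Against Arm 1 with 12 visits the ratio is 0.613/0.718 = 0.85, so the direction reverses. If four GCC visits are added to Arm 2 (an assumed number, *k* = 13), the last ratio becomes 0.746/0.718 = 1.04. In practice *d* would also differ by staff and format, in an unknown direction.

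**4. Effect on the planned test**

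Inputs: 526 randomised (SAP 6), so 526/2 = 263 per arm; an equal true 12-month rate π in both arms (assumed); detection *s*₁ and *s*₂ (assumed). Counts are binomial with probabilities π*s*₁ and π*s*₂. They were enumerated exactly under the SAP 9.7 rule, two-sided 0.05. The apparent risk ratio is *s*₂/*s*₁ whatever π is.

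| Detection | Risk ratio | π = 2% | π = 5% | π = 10% |
|---|---|---|---|---|
| 0.6 vs 0.6 | 1.0 | 1.5% | 5.0% | 5.0% |
| 0.3 vs 0.6 | 2.0 | 2.7% | 19% | 38% |
| 0.4 vs 0.8 | 2.0 | 5.6% | 27% | 49% |

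Entries under π are the share of trials declared significant with no true difference. For 0.3 vs 0.6 at π = 5% the expected counts are 263 × 0.05 × 0.3 = 3.9 and 263 × 0.05 × 0.6 = 7.9.

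**The case against.** The best case for the plan has five parts.

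- **The most serious events do not depend on visits.** Acute-care self-harm and deaths have sources common to both arms. This stands, and the fix relies on it. It does not help ideation or attempts without acute care.
- **Arm 2 contact does not end with CBT.** Participants in both arms have GCC visits for 12 months, and Protocol 6.3.1 treats GCC as part of the Arm 2 intervention. Protocol Table 6 shows intervention visits over months 1 to 12 with no split by arm. On that reading the capture window is the same. This may well be what was meant, but 8.3.5 does not say so, and contact number, format and staff would still differ.
- **The p-value carries little weight.** SAP 7.6 treats every comparison beyond the primary and two key secondary outcomes as descriptive. That limits the consequence, but a descriptive risk ratio is biased in the same way.
- **SAP 9.7 may already mean acute-care suicidality.** Its list of event terms can be read so. SAP 9.2 points the other way, so the wording needs settling.
- **Events should be rare.** Protocol 5.3.2 expects this. At a 2% true rate and a twofold detection gap, the test rejects in only 3% to 6% of trials. The damage is then mainly to the estimate.

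A reader might go further and infer that Arm 2 capture stops at month 3. With 12 months' capture against 3, and true rates of 2%, 4% and 6%, the planned test would reject in 20%, 61% and 81% of trials with no true difference (27% at 4% if Arm 2 capture lasted 6 months). The documents do not support that premise. It sets aside the GCC visits, counts calendar time although capture occurs at visits, and uses event rates that appear nowhere in the plan.

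**Conclusion.** The concern holds for visit-disclosed suicide risk. It is ascertained through contacts that differ by arm, and SAP 9.7 compares it without adjustment or caveat. The comparison therefore mixes detection with harm.

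Neither the direction nor the size of the bias can be derived. Both depend on true rates, disclosure probabilities and Arm 2 visit numbers that the documents do not give, and on whether GCC visits count. The rejection rates above are illustrations. The firmer result is that the apparent risk ratio equals the ratio of detection probabilities when true risk is equal.

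Two broader readings go too far. A reader might infer that suicidality here reflects detection alone, but acute-care self-harm and suicide deaths are captured in both arms independently of intervention visits. A reader might also infer that a participant with no intervention visit cannot have an event. SAP 8.1 says such participants still received survey invitations and EHR extraction, so only a visit-disclosed event is ruled out for them.

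The primary and key secondary analyses are unaffected.

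**What to change.** Amend SAP 9.2 and 9.7:

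1. Split suicidality into (a) visit-disclosed suicide risk and (b) acute-care self-harm (ED or hospital) plus suicide deaths.
2. Report (a) descriptively by arm, without a p-value, beside the number of intervention visits and time from randomisation, and state the ascertainment limitation.
3. Limit the comparison between arms to (b). State in SAP 9.2 that the EHR extraction is a source for acute-care events, in line with Protocol 8.3.5, Protocol Table 11 and SAP 4.7.
4. Reconcile the wider and narrower descriptions of the encounters in 8.3.5, including whether Arm 2 GCC visits count. Also reconcile its three triggers (active ideation or attempt, intent to self-harm, and ideation without qualification) into one reporting definition for the analysis.

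This costs SAP wording only. The downside is that fewer suicidality events enter the tested comparison. Widening prospective capture is no longer a realistic remedy: SAP 4.6 expected the last intervention visits by March 2023, and SAP 6 already cites June 2023 data.
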